6.2 IMPORTANT PROTOCOL VIOLATIONS

Even though no per protocol population is defined, patients with potentially important protocol violations (iPV) will be identified and documented.

Potentially important protocol violations are defined in [Table 6.2:1](#). The final list of iPVs will be confirmed at the last blinded report planning meeting (BRPM) before the database lock at the time of the CTR.

Two separate iPV tables will be created for patients treated before and after the clinical hold and separately for patients with refractory/relapsed AML patients and AML patients in CR.

Table 6.2: 1 Important protocol violations

Category/ Code		Description	Comment/Example	Excluded from
A		Inclusion/Exclusion Criteria		
A1		Criteria related to safety		
A1.1		Patient has condition that may cause additional risk from study medication	EX 7	None
A1.2		Patient has laboratory assessments that may cause additional risk.	EX 2, EX 8-11	None
A1.3		Patient is unable to comply with the protocol	EX 14, EX 21	None
A1.4		Patient has condition that may interfere with evaluation of safety (and/or efficacy)	EX 3-4, EX 6, EX 12, EX 13, EX15, EX 19, EX 20	None
A2		Criteria related to efficacy		
A2.1		Patient does not have trial diagnosis or is not part of the target population	IN 1-3, EX 1, EX 5	None
B		Legal criteria		

Table 6.2: 1 Important protocol violations (cont.)

Category/ Code		Description	Comment/Example	Excluded from
	B1	Informed consent not available/not done	IN 5	All
	B2	Informed consent after visit 1	IN 5	None
	B3	Men or women who are sexually active and not using adequate contraception.	EX 16, EX 17	None
	B4	Pregnant or nursing female patient	EX 18	None
	B5	Patient's age < 18	IN 4	None
C		Administration of trial medication not in accordance with the protocol		
	C1	Administration of trial medication not in accordance with the protocol	As marked in the eCRF, review and decision at medical and quality review meetings (MQRM) / report planning meetings (RPM)	None
	C2	Continuation of treatment although criteria for re-treatment are not met	Create listing, decision at medical and quality review meetings (MQRM) / report planning meetings (RPM), see CTP section 4.1.4	None
	C3	Unjustified intra-patient dose-escalation	Create listing, decision at MQRM / RPM, see CTP section 4.1.4	None
	C4	Withdrawal of patient not performed according to CTP	Create listing, decision at MQRM / RPM, see CTP section 3.3.4	None
	C5	Discontinuation of trial drug not performed according to CTP	Create listing, decision at MQRM / RPM, see CTP section 3.3.4	None
D		Restrictions		
	D1	Additional experimental anti-cancer, chemo-, immuno-, hormone - or radiotherapy during the study or too shortly before the study.	Create listing, decision at MQRM / RPM (section 4.2.2.1 and exclusion criteria #3, #6)	None
E		Missing data		
	E1	Baseline bone marrow assessment not within 14 days prior to first treatment	Create listing, decision at MQRM / RPM	None
	E2	Missing disease assessment at a time point where disease assessment was required	Create listing, decision at MQRM / RPM	None

6.3 PATIENT SETS ANALYSED

- Screened set (SS): This patient set includes all patients who have signed the informed consent. The SS will be used for patient disposition tables.
- Treated set (TS): This patient set includes all patients who were documented to have received at least one dose of trial medication. The TS will be used for all efficacy and safety analyses.

- MTD evaluable set: The MTD set consists of all patients who were entered, treated and considered evaluable for MTD determination.

The above patient sets will be defined separately for refractory/relapsed AML patients and AML patients in CR. However, due to the early enrolment stop of the refractory/relapsed AML patients, the MTD (RP2D) set is not applicable for this patient population. No combined safety analysis of both patient populations is foreseen on trial level. If deemed necessary, this will be performed on project level.

No per protocol population will be used for analyses.

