3 INTRODUCTION

As per ICH E9, the purpose of this document is to provide a more technical and detailed elaboration of the principal features of the analysis described in the protocol, and to include detailed procedures for executing the statistical analysis of the primary and secondary variables and other data.

This TSAP assumes familiarity with the Clinical Trial Protocol (CTP), including Protocol Amendments. In particular, the TSAP is based on the planned analysis specification as written in CTP section 7 "Statistical Methods and Determination of Sample Size". Therefore, TSAP readers may consult the CTP for more background information on the study, e.g., on study objectives, study design and population, treatments, definition of measurements and variables, planning of sample size, randomisation. This TSAP follows the Boehringer Ingelheim (BI) internal reference ([1](#)).

This TSAP is based on the Project SAP wherever possible. Wordings like "randomisation (first administration of study treatment in non-randomised trials)" should therefore be interpreted as applicable.

SAS Version 9.2 or later version will be used for all analyses.

Version 1 of this TSAP(c01837068-02) fully specified the planned analyses for the population of patients with refractory or relapsed AML. Further enrolment of this population was stopped as of 10-JUN-2016 (for more details refer to CTP amendment 3 and the authorisation letter to continue study cohort 3 in AML patients in complete remission with high risk to relapse). In January 2018, the trial was terminated because of low patient recruitment into the CR population. This version now includes the specifications as to how the data from the CR population will be summarized a final CTR that will includes the analyses for both populations.

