4 CHANGES IN THE PLANNED ANALYSIS OF THE STUDY

Clarification of Residual Effect Period (REP):

According to CTP section 6.2.5, for refractory or relapsed AML patients the reporting period for adverse events is defined until 6 weeks (42 days) after last administration of study drug.

However, the residual effect period (REP) for BI 836858 is defined as 30 days. Therefore, for all safety analyses defined in this TSAP, all events occurring between first drug administration until 30 days after last drug administration will be considered on treatment. A separate table or listing will be provided with adverse events outside the on-treatment period. See TSAP [section 7.8](#) for details.

For AML patients in CR a REP of 30 days was defined in the CTP.

For the CR patients, an abbreviated set of tables and listings will be included consisting of:

- Patient disposition
- Patient demographics
- Baseline disease characteristics
- Exposure
- Medication compliance
- Summary table of Adverse Events
- Frequency table of adverse events by highest CTCAE grade
- Frequency table of user defined adverse events by highest CTCAE grade
- Overall summary of infusion related reactions
- Listing of patients with dose related toxicities
- A frequency table of AEs by treatment, system organ class, and preferred term
- Hepatic injury (DILI)
- Listing of hepatic enzymes and bilirubin
- Summary of haemalytic laboratory values

Listings of all clinical efficacy, safety, laboratory and biomarker data will be provided.

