5 ENDPOINTS

5.1 PRIMARY ENDPOINTS

The primary endpoints are the maximum tolerated dose (MTD) and the number of patients with dose limiting toxicity (DLT) during the MTD evaluation period.

Maximum tolerated dose (MTD):

MTD is defined as the highest dose studied for which the incidence of dose-limiting toxicity is no more than 17% (i.e., 1/6 patients) during the MTD evaluation period. The MTD will be defined on the basis of DLTs occurring during the MTD evaluation period of dose escalation cohorts. However, all information, including adverse events qualifying for a DLT from later times, will be considered in the final determination of the recommended Phase II dose (RP2D).

MTD evaluation period:

FOR PATIENTS WITH REFRACTORY OR RELAPSED AML,

the MTD evaluation period is defined as the time from the first administration of BI 836858 to start of the fifth administration, excluding the day of fifth administration. In case the fifth infusion will not be started, the evaluation period ends 30 days after the last administration.

FOR AML PATIENTS IN CR WITH HIGH RISK TO RELAPSE,

the MTD evaluation period is defined as the time from the first administration of BI 836858 to start of the third administration, excluding the day of third administration. In case the third infusion will not be started, the evaluation period ends 30 days after the last administration.

In case a patient has not completed the required number of administrations due to BI 836858 related toxicity, he/she will not be replaced and this will be considered as DLT. However, patients who have not completed the required number of administrations of BI 836858 for reasons other than BI 836858 related toxicity will be replaced.

That is, a patient will be considered evaluable for MTD assessment if he/she received at least 4 (refractory or relapsed patients) or 2 (patients in CR) administrations of BI 836858 or if he/she received less than 4 (refractory or relapsed patients) or 2 (patients in CR) administrations due to DLT.

The MTD estimate after the dose escalation part of the trial will be obtained on the basis of DLTs observed during the MTD evaluation period. However, for those patients who receive more than 4 (refractory or relapsed patients) or 2 (patients in CR) administrations of BI 836858, all AEs that constitute a DLT will be considered in the final determination of the dose recommended for Phase II.

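### Does dropping the MTD set for refractory/relapsed patients distort the planned DLT summary?

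*SAP*

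**What the plan says.** - **SAP 6.3** defines a screened set, a treated set (TS) and an MTD evaluable set, and adds: "The above patient sets will be defined separately for refractory/relapsed AML patients and AML patients in CR". It then says that "due to the early enrolment stop of the refractory/relapsed AML patients, the MTD (RP2D) set is not applicable for this patient population". The label in that sentence, with RP2D in brackets, is not the one used in the definition, and the visible text does not link the two. For the default set it says: "The TS will be used for all efficacy and safety analyses".
- **SAP 5.1** makes the MTD and the number of patients with DLT the primary endpoints. The MTD is "the highest dose studied for which the incidence of dose-limiting toxicity is no more than 17% (i.e., 1/6 patients) during the MTD evaluation period". For refractory/relapsed patients it keeps an MTD evaluation period and an evaluability rule (at least 4 administrations, or fewer because of DLT). Patients who stop early "for reasons other than BI 836858 related toxicity will be replaced". The list of evaluable patients is to be confirmed before database lock.
- **SAP 6.1** keeps the MTD evaluation period for refractory/relapsed patients in Table 6.1:1.
- **SAP 7.4** plans a DLT summary per dose cohort for the MTD evaluation period and the on-treatment period. It leaves replaced patients out of the MTD determination. It also plans a listing of all treated patients with initial dose, a DLT flag for the MTD evaluation period and an evaluability flag.
- **SAP 7** sets frequency-table percentages over all patients in the relevant set, unless otherwise specified.
- **SAP 3 and 4**: version 1 of the SAP "fully specified the planned analyses for the population of patients with refractory or relapsed AML". For the other population, "For the CR patients, an abbreviated set of tables and listings will be included consisting of" a set of items that includes "Listing of patients with dose related toxicities" but no DLT summary by cohort.

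**The concern.** One section withdraws an analysis set while others keep everything that would use it: the evaluability rule, the evaluation period, the confirmed list, the flag and the summary table. Nor can this be put down to text kept only for patients in complete remission (CR). Their output is the abbreviated one, so the cohort summary in 7.4 falls mainly on the refractory/relapsed patients, the population for which 6.3 calls the set not applicable.

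Because 7.4 names no set, a programmer following the defaults would use the TS and divide by everyone in it. The criterion in 5.1 is a DLT incidence, assessed in evaluable patients. Replaced patients stopped for reasons other than drug-related toxicity, so as a rule they enlarge the denominator and add nothing to the numerator. The printed percentage could then be lower than the incidence that 5.1 has in mind, and in a small cohort it could move from above the 17% line to that line. In the table for a primary endpoint of a dose-escalation trial, that deserves a check.

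**Working it through.** **1. The plan's own figure.** Section 5.1 equates 17% with 1 in 6 patients. 1/6 = 16.7%, which rounds to 17% and meets the criterion.

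**2. The denominator effect.** Let E be the number evaluable, R the number treated but replaced, and D the number with DLT in the MTD evaluation period. Assume that replaced patients had no DLT.

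- Rate over evaluable patients: D/E
- Rate over treated patients: D/(E + R)
- Ratio of the second to the first: E/(E + R)

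The SAP states no cohort sizes, DLT counts or numbers replaced, so every count below is an assumption.

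| D | E | R = 0 | R = 1 | R = 2 |
|---|---|---|---|---|
| 1 | 3 | 1/3 = 33.3% | 1/4 = 25.0% | 1/5 = 20.0% |
| 1 | 5 | 1/5 = 20.0% | 1/6 = 16.7% | 1/7 = 14.3% |
| 1 | 6 | 1/6 = 16.7% | 1/7 = 14.3% | 1/8 = 12.5% |
| 2 | 6 | 2/6 = 33.3% | 2/7 = 28.6% | 2/8 = 25.0% |

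The multiplier is 5/6 = 0.833 for E = 5 and R = 1, and 6/7 = 0.857 for E = 6 and R = 1. With R = 0 it is 1, and with D = 0 both rates are zero. Of the four rows, only the one with E = 5 passes from above 17% to that level or below.

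**3. What the effect reaches.**

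- *The primary endpoint.* Section 5.1 defines it as a number of patients with DLT. D is the same in every column.
- *The MTD.* Section 7.4 bases it on non-replaced patients, so it never uses D/(E + R). In the refractory/relapsed population the enrolment stop is the reason given for not applying the set, which is a legitimate decision.
- *A percentage in the 7.4 table.* Section 7.4 promises a summary of patients and mentions no percentage. One appears only by joining two general defaults: the TS for safety analyses (6.3) and percentages over the whole set (7). The second gives way to any other specification.

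**4. Whether the evaluable rate is lost.** The 7.4 listing gives initial dose, the DLT flag and the evaluability flag for each treated patient. Counting the evaluable patients at each dose returns E, and D/E follows.

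**The case for a change.** The strongest case for a change is that this is a primary-endpoint table without a stated denominator, that the direction of any distortion is predictable, and that the remedy is cheap. One sentence in 6.3 could say that evaluable patients are still identified although no MTD is determined. One in 7.4 could show DLTs over evaluable patients beside the number treated. The list and the flag are already planned, so no new data would be needed.

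Much of this stands as a description. The two set names are not linked, 7.4 names no set, and the defaults do lead to the TS if a percentage is printed. It does not follow that the TS figure would be wrong. The evaluable denominator serves the MTD decision. Without that decision, DLTs in this population are descriptive safety data: section 7.8.1 classes them as adverse events of special interest and has them tabulated, and 6.3 assigns safety analyses to the TS. The same 7.4 summary also covers the on-treatment period, for which the TS is the natural base, so one denominator for both periods is coherent. Showing the number evaluable beside the number treated would be a better display, but that is a choice of presentation.

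The inconsistency itself is also less than certain. Text around the patient-set definitions appears to be missing from the public copy, section 6.4 is not visible, and 6.1 refers to technical documents that are not shown. The set with RP2D in its label is probably the MTD evaluable set under a looser name, but the visible text does not settle it.

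**Conclusion.** No change follows. Carried out as written, the plan gives the right number of patients with DLT, leads to no wrong MTD decision, and supplies a listing from which the evaluable rate can be recovered. The possible effect is confined to a descriptive percentage that 7.4 does not itself call for. Under the assumed counts, one replaced patient lowers it by 2.4 percentage points in the mildest case (16.7% to 14.3%) and by 8.3 in the largest (33.3% to 25.0%). It is nil in any cohort without replacements or without DLTs.

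This rests on three assumptions: that replaced patients had no DLT, which fits the replacement rule in 5.1; that the evaluability list and flag are produced for refractory/relapsed patients, since 5.1 and 7.4 exempt nobody; and that no MTD is claimed for that population. If an MTD were claimed after all, 7.4 would still exclude replaced patients from it. What is left is loose naming and an unnamed set, which analysts can resolve when they lay out the table.

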6.5 POOLING OF CENTERS

Not applicable because centre/country is not included in the statistical model.

6.6 HANDLING OF MISSING DATA AND OUTLIERS

If not stated otherwise, missing data will not be imputed and remain missing. Potential outliers will be reported and analysed as observed.

Missing or incomplete AE dates are imputed according to BI standards ([2](#)).

For missing laboratory data at Visit 1 (before the very first administration of study medication) data from preceding visits will be used.

6.7 BASELINE, TIME WINDOWS, AND CALCULATED VISITS

Study days and visits will be labelled according to the CTP's flow chart.

Unless otherwise specified, baseline is defined as the time-point closest to but prior to first administration of trial medication in course 1. Note that for some trial procedures (for example body weight, vital signs, laboratory tests) this may be the value measured on the same day trial medication was started. In these cases it will be assumed that the measurements were taken according to protocol, i.e. prior to first intake of any trial medication.

Laboratory values: Baseline is defined as the latest time-point before the very first administration of any trial medication in course 1. For laboratories where not only the examination date but also time are recorded, examination time has to be taken into account when defining baseline. That is, a laboratory value on the same date as the first trial drug administration is considered as baseline value if and only if the time of laboratory value is before or the same as the time of first trial drug administration.

7 PLANNED ANALYSES

The labelling and display format of statistical parameters will follow the guideline “Reporting of Clinical Trials and Project Summaries” (3).

For End-Of-Text (EoT) tables, the set of summary statistics is: N / Mean / Standard deviation (SD) / Min / Median / Max.

For tables that are provided for endpoints with some extreme data, median, quartiles and percentiles will be preferred to mean, standard deviation, minimum and maximum.

In general, means, medians, and percentiles will be presented to one more decimal place than the raw data and SDs will be presented to two more decimal places. Minima and maxima will be presented to the same number of decimal places as the raw data.

For time-to-event analysis tables, the set of statistics is: Number of patients [N(%)], Number of patients with event [N(%)], Number of patients censored [N(%)], <Time to event> [<unit>] followed by P25 (25th percentile), median + CI, P75 (75th percentile). If not specified otherwise, the duration as well as the time to event will be displayed in months and a final decision will be made at the last RPM.

Tabulations of frequencies for categorical data will include all possible categories (even if with no count and also the missing category if there is missing data) and will display the number of observations in a category as well as the percentage (%) relative to the number of patients in the respective treatment group (unless otherwise specified, all patients in the respective patient set whether they have non-missing values or not). Percentages will be rounded to one decimal place. The category missing will be displayed only if there are actually missing values.

If a table presents only categorical data, “N (%)” will be displayed in the column header only.

Abbreviations (e.g., Wors.) or acronyms (e.g., PD) will not be displayed in tables and Subject Data Listings (SDLs) without any explanation. They will be either spelled out or explained in footnotes.

If applicable, conversion from days to weeks, months and years will be as follows:

- Weeks = days \div 7
- Months = 12 \times days \div 365.25
- Years = days \div 365.25

7.1 DEMOGRAPHIC AND OTHER BASELINE CHARACTERISTICS

Standard descriptive analyses and summary tables are planned for this section of the report. Data will be summarized by treatment group and a “total” column will be included in the summary tables.

7.2 CONCOMITANT DISEASES AND MEDICATION

Only descriptive statistics are planned for this section of the report.

Concomitant diseases will be coded similarly as adverse events based on the most current MedDRA version. Concomitant therapies will be coded according to WHO DD. Concomitant therapies (CT) will be classified according to the Anatomical, Therapeutic, Chemical (ATC) classification system. The third ATC level will be used to categorise CTs by therapy type. In situations where a medical product may be used for more than one equally important indication, there are often several classification alternatives. As appropriate, patients receiving CTs with more than one possible ATC level-three category will be counted more than once; footnotes will clarify this possible double counting in tables.

7.3 TREATMENT COMPLIANCE

Only descriptive statistics are planned for this section of the report.

7.4 PRIMARY ENDPOINTS

The primary endpoints are the MTD and the occurrence of DLT. The MTD is determined from the number of non-replaced patients with DLT during the MTD evaluation period (for the definition of MTD evaluation period refer to [section 5.1](#)).

An overall summary of patients with DLT(s) which occurred during the MTD evaluation period and the on-treatment period will be provided for each dose cohort.

Patients who were treated but replaced are not considered for the MTD determination. However, all information, including adverse events qualifying for a DLT from later times, will be considered in the final determination of the recommended Phase II dose (RP2D).

In order to describe the occurred dose escalation steps, a listing of all treated patients will be provided. This will include the initial dose of the investigational medicinal product, patient number, treatment start date, DLT in MTD evaluation period [y/n], Evaluable for MTD [y/n] and will be sorted by treatment start date.

7.5 SECONDARY ENDPOINTS

7.5.1 Key secondary endpoint(s)

This section is not applicable as no key secondary endpoint has been specified in the protocol.

7.5.2 Other secondary endpoint(s)

Best overall response:

Best overall response will be analysed descriptively. The number of treated patients and the frequency of patients by best overall response category including the corresponding percentages will be presented.

Progression-free survival (PFS) and Time to treatment failure (TTF):

PFS and TTF will be assessed based on the Kaplan-Meier method. Point estimates together with confidence intervals (based on Greenwood's method) will be provided for median PFS (if applicable). The Breslow method for handling ties will be used. The censoring rules for PFS are as stated in [Section 5.2.2](#).

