6 GENERAL ANALYSIS DEFINITIONS

6.1 TREATMENTS

In this Phase I trial, treatments are not randomised (open-label, dose escalation). Different dose levels of the investigational medicinal product can arise. The data will be presented for all dose cohorts separately, in particular patients will be analysed by the treatment group initially assigned in the first treatment course.

“Analysing treatment” will be used for reporting of treatment emergent adverse events (AE) and to differentiate between screening, on-treatment, post-treatment and post-study safety data. The inequalities start date \leq onset date of AE $<$ stop date will determine whether the AE will be assigned to the “analysing treatment” or not. [Table 6.1: 1](#) defines the “analysing treatment period(s)” which will be used for reporting of treatment emergent AEs and safety laboratory parameters.

Table 6.1:1: Definition of analysing treatment periods

Analysing treatment period	Start date (including)	Stop date (excluding)
Screening	Date of informed consent	Date of first administration of trial medication
On-treatment	Date of first administration of trial medication	Start date of ‘Follow-up’
Follow-up	Date of end of REP +1	Start date of ‘Post-study’
Post-study	Last date patient status obtained / last date patient known to be alive + 1 (if patient is lost to follow-up) / date of refusal + 1 day / the date patient died + 1	During the trial: open / empty; after database lock (DBL): DBL + 1 day
MTD evaluation period	Date of first administration of trial medication	For patients with refractory/relapsed AML: Date of fifth infusion or (if the fifth infusion was not administered) Date of last administration of trial medication + 30 days + 1 day For AML patients in CR: Date of third infusion or (if the third infusion was not administered) Date of last administration of trial medication + 30 days + 1 day

Data recorded between the first administration of trial medication until up to 30 days (Residual effect period; REP) after the last administration of trial medication will be considered as on-treatment.

In addition, to justify the MTD determination, AEs occurring during the MTD evaluation period will be presented separately from those occurring during the complete on-treatment period.

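### Does the SAP misuse Greenwood's method and Breslow's tie rule for the confidence interval of median PFS?

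*SAP*

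**What the plan says.** Section 7.5.2 fixes the estimator: "PFS and TTF will be assessed based on the Kaplan-Meier method". On precision it says that "confidence intervals (based on Greenwood's method) will be provided for median PFS", alongside point estimates and only where applicable. It adds: "The Breslow method for handling ties will be used". Section 7 lists the contents of time-to-event tables in general and includes "median + CI, P75 (75th percentile"), so an interval is expected for TTF as well as PFS.

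The readable SAP gives no confidence level, no scale for the limits, and no rule for passing from limits on the survival curve to limits on the median. It describes no Cox or other regression for PFS or TTF. The one mention of a model, in Section 6.5, is generic: "Not applicable because centre/country is not included in the statistical model".

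On the size of the groups, Section 6.1 says that "The data will be presented for all dose cohorts separately". No cohort size is given as a number. The nearest indication is the MTD rule in Section 5.1, under which "the incidence of dose-limiting toxicity is no more than 17% (i.e., 1/6 patients").

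**The concern.** Greenwood's formula gives a standard error for the survival estimate at a chosen time. An interval for the median needs two further choices: an inversion rule (the Brookmeyer-Crowley approach) and a scale on which the limits are formed. The SAP makes neither. If a programmer formed the limits as the estimate plus or minus 1.96 Greenwood standard errors, the interval could be too narrow in cohorts of phase I size, which is the level at which results are shown.

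Breslow's method deals with tied event times in a Cox partial likelihood. Kaplan-Meier handles ties itself, so the sentence suggests either a missing model or text carried over from elsewhere.

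At stake would be the stated precision of the secondary time-to-event results: an interval labelled 95% that covers the true median noticeably less often.

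**Working it through.** The SAP states no coverage, power or sample size for PFS, so it has no figure to reproduce. The check asks how much the unstated scale matters.

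**Inputs.** Variance: Greenwood (Section 7.5.2). Level: two-sided 95%, z = 1.96 (assumed). Cohort size n: 3 to 30 (assumed; Section 5.1 points to about 6). Censoring: none, 20% or 30% (assumed).

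**Rule.** The interval is the set of times at which 0.5 lies within the limits for S(t).
- Plain scale: |S − 0.5| ≤ 1.96 × SE.
- Log-log scale: |log(−log S) − log(−log 0.5)| ≤ 1.96 × √v / |log S|.

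Without censoring, after k events S = 1 − k/n, SE = √(S(1 − S)/n) and v = 1/(n − k) − 1/n. The number of events before the true median is Binomial(n, 0.5) whatever the event-time distribution, so coverage is exact.

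**n = 6, plain scale.**
- k = 1: S = 0.833, SE = √(0.1389/6) = 0.152. Lower limit 0.833 − 0.298 = 0.535, which excludes 0.5.
- k = 5: by symmetry, upper limit 0.167 + 0.298 = 0.465, also excluded.
- k = 2, 3, 4 are included, so the interval runs from the 2nd to the 5th event.
- Coverage = (15 + 20 + 15)/64 = 50/64 = 78.1%.

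**n = 6, log-log scale.**
- k = 1: v = 1/5 − 1/6 = 0.0333. Distance |−1.702 + 0.367| = 1.335; allowance 1.96 × 0.1826/0.1823 = 1.963. Included.
- k = 5: v = 1 − 1/6 = 0.833. Distance 0.583 + 0.367 = 0.950; allowance 1.96 × 0.9129/1.7918 = 0.999. Included.
- k = 1 to 5 are all included. Coverage = 62/64 = 96.9%.

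**Other sizes, no censoring, exact.**

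| n | Plain | Log-log |
|---|---|---|
| 3 | 75.0% | 75.0% |
| 4 | 87.5% | 87.5% |
| 5 | 93.8% | 93.8% |
| 6 | 78.1% | 96.9% |
| 8 | 93.0% | 96.1% |
| 10 | 89.1% | 94.4% |
| 12 | 85.4% | 97.8% |
| 15 | 88.2% | 93.7% |
| 20 | 95.9% | 97.3% |
| 30 | 95.7% | 95.7% |

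Here the interval is closed at the last event when the curve reaches zero. Leaving it open raises n = 3 to 87.5% on both scales.

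**With 20% / 30% censoring** (10,000 simulated exponential samples per setting):

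| n | Plain | Log-log |
|---|---|---|
| 3 | 69.0% / 64.7% | 69.0% / 64.7% |
| 6 | 81.5% / 82.9% | 94.7% / 92.9% |
| 12 | 90.0% / 90.0% | 96.6% / 96.0% |
| 20 | 92.4% / 92.6% | 95.4% / 95.6% |
| 30 | 93.3% / 93.3% | 95.2% / 95.2% |

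**Reading.** Both columns use Greenwood's variance and both fit the SAP's wording. The scale matters from about 6 to 15 patients, not at all at 3 to 5, and by a few points at most from 20 upward.

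**Breslow.** With Kaplan-Meier as the only method described, the sentence enters no formula above. Keeping or deleting it gives the same estimate, interval and table.

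**The case for a change.** The best case for a change is that Section 3 gives the SAP the task of technical elaboration, so the interval method should be settled there. In a cohort of 6 the open choice separates 78.1% from 96.9% coverage, and an unstated choice in an open-label trial can be made after the data are seen. Section 7.5.2 also names a method for the PFS median only, although Section 7 expects an interval for TTF. Two or three sentences would settle all this and remove a sentence that has no function.

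Part of this stands. The scale is not named, TTF is not mentioned alongside the interval method, and the Breslow sentence has nothing to act on in the readable text.

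The charge of a misapplied method does not stand. The SAP says the interval is based on Greenwood's method, and the log-log remedy is based on it too. The charge that intervals will be too narrow does not stand either, because it assumes untransformed limits that the SAP does not specify. In the smallest cohorts, where poor coverage is most likely, naming the log-log scale would change nothing.

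Two limits apply to the criticism itself. Parts of the SAP are removed, including the section between 7.5.2 and 7.7, so the absence of a Cox model can be asserted only of the readable text. The confidence level may stand in the protocol's statistical section, on which Section 3 says the plan is based.

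**Conclusion.** No change is needed. The median interval is under-specified, not wrong, and an analyst can meet the present wording soundly by inverting Greenwood-based limits on a transformed scale and treating TTF in the same way, since Section 5.2.2 derives the two endpoints alike.

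The largest effect found is 96.9 − 78.1 = 18.8 percentage points of coverage at n = 6 without censoring, and it arises only if plain limits are chosen. It is nil at n = 3 to 5 and at n = 30 without censoring. These figures rest on an assumed 95% level, assumed cohort sizes and, in the censored cases, exponential event times.

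Little depends on the interval. The primary endpoints are MTD and DLT (Section 7.4). PFS is a non-key secondary endpoint with no test attached, and the words on applicability allow the interval to be left out where a cohort is too small. The abbreviated set of tables for patients in CR (Section 4) contains no PFS or TTF table, so the point mainly concerns the refractory or relapsed population, whose enrolment had already stopped (Section 3).

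The Breslow sentence is best read as a clerical leftover, possibly from the Project SAP on which Section 3 says this plan draws. It is harmless.
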